Older adults with impaired fasting glucose (IFG) will be randomized to into a double-blinded, placebo-controlled intervention study with metformin. This clinical trial has the primary outcome of change in appendicular lean mass and physical performance assessed between baseline and year 3 based on our prior observational findings above and Power calculations below. The secondary outcome of change in muscle histology over 6 months using muscle biopsies is planned in a substudy of participants given previous studies that show significant biological effects on muscle with metformin treatment during this time interval.^{32, 61}

Study Population

Inclusion criteria: 120 randomized, sedentary, weight-stable, ambulatory men and women 65 years or older with pre-diabetes identified with IFG (100 mg/dL \leq fasting glucose<126 mg/dL) on no diabetes medications. Participants must demonstrate that they are able to ambulate 400 meters without assistance. Participants must be able to fast for 12 hours prior to blood draw.

Subjects who meet the above inclusion criteria and meet the additional exclusion criteria for the Muscle Biopsy Substudy listed below will be considered for enrollment (32 subjects) in the muscle biopsy substudy.

Exclusion criteria: Participants will be excluded if they plan to move away from the Portland metropolitan area during the 3 year study time frame. Participants with conditions that are relative contraindications to metformin or affect muscle mass or performance measurements will be excluded as outlined below. Specific criteria are delineated below.

Exclusion Criteria

- 1. Chronic medical conditions affecting muscle mass or function
 - a. Active non-skin cancer
 - b. Hypogonadism
- 2. Medications affecting muscle mass or function See section "Prohibited Medications."
- 3. Lifestyle factors affecting muscle
 - a. Intentional/unintentional weight loss
 - b. Vigorous regular exercise
- 4. Contraindications to metformin
 - a. Renal dysfunction defined as creatinine $\geq 1.5~mg/dL$ for men or $\geq 1.4~mg/dL$ for women or eGFR< 60 mL/min
 - b. Liver dysfunction defined as ALT > 48 U/L, AST > 41 U/L
 - c. B12 deficiency defined as B12 level < 180 pg/mL
 - d. Congestive heart failure
 - e. Known hypersensitivity to metformin
 - f. Excessive alcohol intake (average of ≥ 2 alcoholic beverages/day over a month)
 - g. Serious medical condition in the opinion of the investigator

Additional Exclusion Criteria for Muscle Biopsy Substudy

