Initial contact with potential subjects will occur in clinic, by phone or by mail. If in clinic, their provider will approach them first to see if they are interested in the study and ask if they agree to be contacted by study personnel. If the patient agrees, they can initiate contact with the study team by phone or have the study coordinator speak to them in clinic or call them later. If initial contact is by phone, potential subjects can contact the study coordinator directly using information on the advertising flyers. If initial contact is by mail, potential subjects will receive a recruitment letter indicating the option to opt out by returning an included letter indicating the wish to not be contacted again. The letter will state that if a response is not received within two weeks, potential subjects may be contacted by phone. Included with this mailing will be an approved informational letter from the Chief of Primary Care.

During the screening telephone call, a study coordinator will discuss the inclusion and exclusion criteria and provide further details on the study. If participants are interested and are potentially eligible, a Screening visit will be scheduled.

Study design

The proposed study duration of 3 years has been selected based on our prior observational findings over 3.5 years.²⁵ Eligible participants will have an initial Baseline visit, followed by randomization to placebo or metformin (Fig. 7). Between visits, telephone surveying of medication compliance will be obtained and any AEs reviewed. Participants will be seen every 6 months, and have annual study visits for measurements of muscle mass and performance. A substudy of participants will also include muscle biopsies at 2 visits; within 14 days from baseline and at the 6 month visit.

9

Primary outcome measures

To test the primary hypothesis that metformin-treated participants will have a slower decline in muscle mass and physical performance than those on placebo, we will be measuring total and appendicular lean mass using dual x-ray absorptiometry and assessing physical performance with the short physical performance battery (SPPB), grip strength and a 400 meter walk. Our preliminary findings suggest that there should be attenuation in the loss in appendicular lean mass and gait speed, and additional performance measures will be explored.

Secondary outcome measures

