The payments are reasonable and commensurate with the expected contributions of the subject. Each annual study visit is 2-3 hours. Baseline and annual visits include a fasting blood draw, height, weight, blood pressure, questionnaires, performance tests, and DXA. The procedures at every 6 month study visits (in between annual visits) are only fasting labs and questionnaires for all participants. For the muscle biopsy substudy, there will be a separate 1-2 hour visit at baseline and an additional 1 hour added to the 6 month visit.

Payments are fair and appropriate and do not constitute (or appear to constitute) undue pressure or influence on, or coercion of, the prospective research subjects to volunteer for or continue participation in the research study.

Statistical considerations

Sample Size and Power

Based on prior observational findings, there was a significant difference (2.2%, p< 0.01) in the percentage change in appendicular lean mass over 3.5 years between metformin-treated and untreated men. The sample size required for 80% Power to detect this difference and reject the null with SD=4% and α =0.05 for an unpaired, 2-sided t-test is 106 study participants (53 in each group). We plan to enroll 300 participants and, of those, randomize 120 (60 in each group) to allow for potential drop outs due to noncompliance and other reasons (7.5-10%). While 8-11% of participants may

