progress to diabetes yearly,^{72, 79, 80} all efforts will be made to retain these participants in the study and to include them in intent-to-treat analyses. The Power and effect size estimates for gait speed (SD=0.19) for α =0.05 for 60 participants and 53 participants per group are illustrated in the graph (Fig. 8) and based on our preliminary data in older women. The sample size of 60 participants per group will have 73% Power to detect a 0.09 m/s difference in gait speed. Within each group, 16 participants will be randomly selected and consented to undergo muscle biopsies at baseline and 6 months for secondary analyses of muscle histologic changes with metformin vs. placebo treatment. There is an expected change in these histologic measures within 6 months given prior studies that detect changes in AMPK activation, ATP concentration and insulin sensitivity prior to 6 months with use of metformin.^{3, 4} Estimated effect sizes of the difference in histologic measures between the two groups after 6 months are shown below in Table 3. While this study is adequately powered for 3 year outcomes in muscle loss, interim analyses may be performed by a Data Monitoring Committee (managed by the VA CSRD), given blinding of the primary investigator to the intervention, and the trial may be terminated early if a significant difference in the primary outcome between metformin- and placebo-treated groups is noted before 3 years.

	SD	70%	80%	90%
Capillary Density (AU)	0.35	0.32	0.36	0.42
IMCL (AU)	0.50	0.46	0.51	0.59
SDH (AU)	0.50	0.46	0.51	0.59
% Type I Fibers	24.0	21.8	24.6	28.4

Table 3 Estimated detectable difference in muscle histology measures at 80 and 90% Power

SD derived from measures in older insulin-resistant adults³⁶

Statistical Analyses

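### Lean mass and physical performance are both primary, each powered at 0.05, but no rule says which results make the trial positive

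*Combined protocol and SAP*

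**What the plan says.** The Overview under Research Design and Methods joins two domains in one primary outcome: "This clinical trial has the primary outcome of change in appendicular lean mass and physical performance assessed between baseline and year 3". It adds that this choice is "based on our prior observational findings above and Power calculations below".

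The section on primary outcome measures lists total and appendicular lean mass, the SPPB, grip strength and the 400 m walk. It then singles out two measures: "there should be attenuation in the loss in appendicular lean mass and gait speed, and additional performance measures will be explored".

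Sample Size and Power treats those two separately. For ALM it takes a 2.2-point difference in percentage change, SD 4% and two-sided 0.05, giving 53 per group for 80% power. It randomizes 60 per group to allow for 7.5-10% dropout. For gait speed it uses 0.05 again with SD 0.19: "The sample size of 60 participants per group will have 73% Power to detect a 0.09 m/s difference in gait speed".

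Statistical Analyses calls these primary outcomes, in the plural, and models each measure separately with a time-by-group interaction. None of these sections gives an order of testing, a division of alpha, or a statement of whether one or both outcomes must be significant.

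**The concern.** The plan can be followed in at least three ways: either outcome can carry the trial, both must succeed, or ALM leads and performance follows. The first has a false-positive rate above 5%. The second has less power than either figure the protocol reports. The third has neither problem but is not written down.

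The choice matters most when only one outcome is significant. The Background anticipates that case: it cautions that gains in muscle mass need not bring gains in strength or function and may then matter little clinically. Without a rule, whether such a trial is positive could be settled after the results are known.

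The gap also touches the provision for early termination. It depends on a significant difference in the primary outcome, in the singular, without naming it.

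**Working it through.** **Inputs.** From Sample Size and Power: ALM difference 2.2, SD 4, so d = 2.2/4 = 0.55; gait speed difference 0.09, SD 0.19, so d = 0.09/0.19 = 0.474; two-sided alpha 0.05 for each (the protocol states two-sided for ALM; taken as two-sided for gait speed, which reproduces its 73%); 60 randomized per group. Completers: 60 × 0.90 = 54 and 60 × 0.925 = 55.5, so 54-55 per group. The correlation between the two outcomes is not in the documents; 0 to 0.7 is assumed.

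**Step 1: reproduce the plan's figures.** Two-sample t-test, power = P(|T| > critical t), where T is noncentral t with 2n − 2 degrees of freedom and noncentrality d√(n/2).

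| n per group | ALM power | Gait speed power |
|---|---|---|
| 53 | 80.1% | 67.6% |
| 54 | 80.8% | 68.4% |
| 55 | 81.6% | 69.2% |
| 60 | 84.8% | 73.0% |

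The stated 80% at 53 and 73% at 60 are both correct as single-test figures.

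**Step 2: either can win.** At correlation 0, familywise error is 1 − 0.95² = 9.75%. For correlated outcomes it is the bivariate normal probability that at least one |Z| exceeds 1.96: 9.5% at correlation 0.3, 9.1% at 0.5 and about 8.4% at 0.7.

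**Step 3: both must win.** At correlation 0, joint power is the product of the two powers. At 0.7 it is the bivariate normal probability with the same two marginal powers.

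| n per group | Correlation 0 | Correlation 0.7 |
|---|---|---|
| 54 | 0.808 × 0.684 = 55.3% | 63.5% |
| 55 | 0.816 × 0.692 = 56.4% | 64.4% |
| 60 | 0.848 × 0.730 = 61.9% | 68.8% |

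Requiring both does not inflate type I error.

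**Step 4: exactly one significant, both planned effects real.** This is the sum of the two powers minus twice the joint power. At n = 54: 0.808 + 0.684 − 2 × 0.553 = 38.6% at correlation 0, and 1.492 − 2 × 0.635 = 22.2% at 0.7. At n = 55: 1.508 − 2 × 0.564 = 38.0%, and 1.508 − 2 × 0.644 = 22.0%. The range is about 22-39%.

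**Step 5: power under Holm.** The smaller p-value is tested at 0.025 and, if that succeeds, the larger at 0.05. An outcome succeeds if its p is below 0.025, or if its p lies between 0.025 and 0.05 and the other is below 0.025. Single-test power at 0.025 is 71.1% (ALM) and 56.7% (gait speed) with 53 per group, and 77.0% and 62.8% with 60. At correlation 0:
- ALM, n = 53: 0.711 + (0.801 − 0.711) × 0.567 = 76.2%
- ALM, n = 60: 0.770 + (0.848 − 0.770) × 0.628 = 81.9%
- Gait speed, n = 53: 0.567 + (0.676 − 0.567) × 0.711 = 64.4%
- Gait speed, n = 60: 0.628 + (0.730 − 0.628) × 0.770 = 70.7%

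Simulation with one million draws per setting over correlations 0 to 0.7 gives ALM 74-76% (53) and 80-82% (60), gait speed about 64% and 70-71%, and familywise error 4.3-5.0%. If only ALM responds, its power is about 71% (53) or 77% (60).

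**Step 6: power under a fixed sequence, ALM first.** ALM keeps its single-test power. Gait speed has the joint power: 54-62% (53) or 62-69% (60). If only gait speed responds, it can be claimed in at most about 0.05 × 0.676 = 3.4% (53) or 0.05 × 0.730 = 3.7% (60) of trials, falling to 2.7% at correlation 0.7.

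**The case against.** **The word joining the two domains means both must succeed.** This is a fair reading, and under it no error inflation arises. But no section says so, and no joint power is reported. A reader who assumes it has to replace 80% and 73% with a lower figure.

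**ALM plainly leads.** This has some force. The trial is sized on ALM, and the sentence permitting early termination opens by describing the study as adequately powered for muscle loss over three years. It would therefore be too strong to call the stopping outcome wholly undetermined. Still, this is a hint and not a hierarchy: Specific Aims, the Overview, the primary outcome measures and the analysis section all give performance the same rank as mass.

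**The measures listed as primary give more than two ways to win.** A reader might infer this and compute a larger error: with ALM, SPPB, grip strength and the 400 m walk each able to win, about 13% (correlation 0.7) to 18.5% (independent). The documents do not support that count. The same section singles out ALM and gait speed and says further performance measures are to be explored, so two outcomes is the fair reading.

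**The power figures are not those of the planned analysis.** This stands. A reader might infer that power for both can never exceed 73%. That ceiling belongs to the sizing t-test with 60 per group. The planned mixed model uses four visits and retains participants with incomplete follow-up, and its power cannot be derived from the documents.

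**The stakes are limited.** The protocol says the study is not meant to support a significant labelling change. That argues for a lower severity; it does not supply the missing rule.

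**Conclusion.** The concern holds as a missing decision rule for two primary outcomes. The two single-test power figures are correct; what is absent is how the two results combine. The plan as written leads either to about 8-10% familywise error or to joint power of about 55-64% after planned dropout. A split result is a realistic outcome that the plan does not classify.

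These sizes rest on three assumptions: only ALM and gait speed count, their correlation lies between 0 and 0.7, and power follows the protocol's own t-test basis. They exclude any interim looks.

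This should be fixed, but it does not invalidate the design. One plausible reading has no error inflation, the sizing already hints at ALM, and the remedy is wording alone.

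**What to change.** In the Overview, the primary outcome measures and Statistical Analyses, name change in ALM and change in 6-metre gait speed from baseline to year 3 as the two primary outcomes. Control familywise error at two-sided 0.05 with Holm, which keeps the equal standing of mass and function. Restate power with both effects real as ALM about 74-76% (53 per group) or 80-82% (60), and gait speed about 64% or 70-71%. Give also the ALM figure if only ALM responds: about 71% or 77%.

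If the sponsor intends ALM to lead, state a fixed sequence: ALM at 0.05, then gait speed at 0.05 only if ALM is significant. ALM power stays at 80% with 53 per group. Gait speed power becomes 54-62% (53) or 62-69% (60), and a benefit confined to gait speed could be claimed in only about 3-4% of trials. If both outcomes are required, say so and restate the joint power.

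In each case:
- Label total lean mass, SPPB, grip strength and the 400 m walk secondary or exploratory.
- State which outcome the early-termination sentence means.
- Fix one tested quantity in advance: the year-3 treatment contrast in change from baseline, which matches the Overview and the sizing calculation.

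The cost is text and the restated power. No participants, visits or measurements are added.

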Physical Performance Tests: Performance tests will occur at VAPORHCS and OHSU. They will be conducted at Screening, Baseline, and the annual visits. At Screening, subjects must demonstrate they are able to walk 400 meters. At Baseline and the annual visits, assessments of grip strength, a 400 meter walk, timed 6 meter walk, all of the short physical performance battery (SPPB) tests, and Instrumented Sway (ISway) test will be conducted. All performance tests will be instrumented with Mobility Lab sensors on bilateral upper and lower extremities, waist and chest using elastic straps. The ISway test consists of 3 trials where the participant stands for 30 seconds without moving with their arms at their side. Each trial will have measures of amplitude, velocity, frequency and jerkiness of postural sway in lateral and anterior-posterior directions with 42 metrics. The SPPB comprises tests of balance, timed walk and chair stands and is predictive of subsequent disability in older adults.¹¹ For tests of

balance, the ability and/or duration (s) in which a participant can maintain a tandem, semi-tandem and side-byside stand will be recorded. Participants will be timed in the task of rising from a seated position 5 times in rapid succession without use of their arms. Those who are unable to complete this task without the use of their arms will be considered unable. The participant's time to complete a 6 meter walking course at his/her usual pace will be measured with a stopwatch. Walking speed (meters/second) will be determined from the better of two trials. In addition to the SPPB, tests of endurance and strength will assessed with a 400 meter walk and grip strength. The time to complete a 400 meter walk test will also be measured with a stopwatch. Participants will be considered unable to perform this task if they require more than 15 minutes for the 400 meter walk or if they require use of assistance. Grip strength will be assessed using a Jamar dynamometer in the participant's dominant hand.⁷³ The maximum effort from two trials will be taken as the measurement of maximum grip strength (kilograms).

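### The primary physical performance endpoint is not uniquely defined, and only walking speed has a power statement

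*Combined protocol and SAP*

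**What the plan says.** All references are to the combined protocol and SAP.

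- **Overview (Research Design and Methods):** "This clinical trial has the primary outcome of change in appendicular lean mass and physical performance", measured from baseline to year 3. No performance test is named, but the sentence goes on to rest this choice on the observational findings described earlier and the power calculations given later.
- **Primary outcome measures:** the primary hypothesis of slower decline is tested by measuring lean mass and by "assessing physical performance with the short physical performance battery (SPPB), grip strength and a 400 meter walk". The next sentence says the preliminary findings lead the investigators to expect "attenuation in the loss in appendicular lean mass and gait speed, and additional performance measures will be explored".
- **Physical Performance Tests (Study Procedures):** "The SPPB comprises tests of balance, timed walk and chair stands". Within the account of those tests, the participant's "time to complete a 6 meter walking course at his/her usual pace will be measured with a stopwatch", and "Walking speed (meters/second) will be determined from the better of two trials". The section then continues: "In addition to the SPPB, tests of endurance and strength will assessed with a 400 meter walk and grip strength". Its opening list of assessments also gives the timed 6 m walk as its own item, next to the SPPB tests.
- **Sample Size and Power:** "The sample size of 60 participants per group will have 73% Power to detect a 0.09 m/s difference in gait speed", with SD 0.19 and alpha 0.05. No other performance measure is given an SD, an effect size or a power figure in the text.
- **Statistical Analyses:** muscle mass and performance, each measured at baseline and years 1, 2 and 3, are analysed in separate mixed models. None of the performance measures is identified as primary.

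**The concern.** The sentence that lists how performance is assessed for the primary hypothesis omits gait speed as an outcome in its own right. Gait speed is the measure with the metformin rationale and the power calculation. The sentence after it puts gait speed first and makes the additional measures exploratory. The two sentences imply different endpoints, and the analysis section does not choose between them.

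Two things are at stake. First, if the measures disagree at year 3, the same data could be reported as a positive or a negative primary performance result, depending on which sentence is followed. Second, Sample Size and Power allows the trial to end early if the groups differ significantly on the primary outcome. A Data Monitoring Committee reading this plan cannot tell which performance variable that refers to.

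This is a question of which variable is primary. How alpha is shared between lean mass and performance is a separate matter.

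**Working it through.** **1. Reproduce the stated power.** Inputs from Sample Size and Power: difference 0.09 m/s, SD 0.19, 60 per group, alpha 0.05. The two-sided unpaired t-test is stated there for lean mass; I assume it also applies to gait speed.

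- Standardized effect: d = 0.09 / 0.19 = 0.474.
- Noncentrality: d / √(2/n) = 0.474 / √(2/60) = 0.474 / 0.183 = 2.59, with 2 × 60 − 2 = 118 degrees of freedom.
- Power from the noncentral t: **73.0%**. The normal approximation gives 73.7%. A one-sided test would give 82.5%, which does not match.

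The plan's 73% is therefore correct for a two-sided comparison of walking speed. At 53 per group, the smaller size for which the plan also presents gait-speed power, the same formula gives 67.6%. Reaching 80% would take about 71 per group.

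**2. Ask which variable the 73% belongs to.** The effect is in m/s. The Physical Performance Tests section derives a speed in m/s only from the 6 m usual-pace walk.

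| Candidate | How it is recorded | SD, effect or power in the text |
|---|---|---|
| 6 m walking speed | m/s | SD 0.19, 0.09 m/s, 73% |
| SPPB total | balance, timed walk and chair stands combined | none |
| Grip strength | kg, maximum of two trials | none |
| 400 m walk | time, or unable | none |

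The 6 m walk is described within the SPPB, so the 73% covers one component of a listed measure. The battery also contains balance and chair stands, so power for walking speed is not power for the battery.

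**3. Could power be found for the other three?** Not from the documents, because neither an SD nor an effect is given. To show how far the answer depends on the missing figure, take assumed standardized effects at 60 per group, two-sided alpha 0.05:

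| Assumed effect (SD units) | Power |
|---|---|
| 0.2 | 19% |
| 0.3 | 37% |
| 0.4 | 58% |
| 0.5 | 78% |

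The 73% carries over to another measure only if its standardized effect is also about 0.47. Nothing in the text says whether it is.

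**4. Weigh the sections against each other.** Three places point to gait speed: the Overview, through its reference to findings and power; the second sentence under Primary outcome measures; and Sample Size and Power. One place points to the SPPB, grip strength and 400 m walk: the first sentence under Primary outcome measures. Statistical Analyses is silent. Gait speed is the likelier intention, but no sentence designates it.

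**The case against.** The best defence is that the plan already means gait speed. The Overview bases the primary outcome on the observational findings and the power calculations. For metformin these are appendicular lean mass in men and 6 m walk speed in women, and the two powered measures are lean mass and gait speed. On this reading the first sentence under Primary outcome measures merely lists instruments, and the second says where the effect is expected and that the rest is exploratory.

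Much of this stands, and it is why the fix below follows the plan's own direction. It does not close the gap. The second sentence states an expectation rather than designating an endpoint, it sits directly after a list that omits gait speed, and the analysis section never takes it up.

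Three stronger readings are tempting and are not supported:

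- A reader might infer that the 73% applies to none of the listed measures. That is wrong, because the timed walk is a component of the SPPB, the first measure listed.
- A reader might infer that the other measures are underpowered, for instance by assuming that metformin affects them only through gait speed and choosing a correlation. The documents give no such pathway and no correlation. Their stated mechanism acts on the muscle itself, so the standardized effects could be smaller or larger than 0.47.
- A reader might suspect an arithmetic error. There is none.

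**Conclusion.** The point holds as a defect of definition. The plan leaves four candidate primary performance variables and powers one of them. The 73% (67.6% at 53 per group) is right for walking speed and says nothing about an SPPB total, grip strength or 400 m time, whose power is unknown rather than known to be low. The defect should be corrected, because it leaves room to select the outcome after the fact and makes the early-termination criterion ambiguous for performance. It does not affect the lean-mass endpoint or its sample size.

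The check assumes that the two-sided t-test stated for lean mass also underlies the gait-speed figure, which the match at 73.0% supports. The text does not say whether SD 0.19 refers to walking speed or to its change. The power graph (Fig. 8) was not available; the text describes it as covering gait speed.

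**What to change.** Make the same designation in three places, before any unblinded comparison:

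- **Overview and Primary outcome measures:** state that the single primary performance measure is change from baseline to year 3 in 6 m usual-pace walking speed, in m/s, from the better of two trials as defined under Physical Performance Tests. Label SPPB total, grip strength and 400 m walk time as the additional, exploratory measures.
- **Statistical Analyses:** identify the walking-speed model as the primary performance analysis and the other performance models as exploratory.

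This follows the plan's own rationale and power calculation and fixes what the primary outcome means for performance at an interim look. If the investigators prefer to keep another measure as primary, they should give its SD, effect size and power.

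All these measures are already collected at baseline and every annual visit, so the cost is wording. The downside is that the other three results become supportive only. The change does not raise the 73%.
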